7.2.1 Interim Efficacy Analysis

The efficacy analysis is based on Simon 2 stage optimal design and will be performed after the enrollment of the first 9 evaluable subjects. If there are no responders with CR from the first 9 evaluable subjects (at the 8 week or 16 week response assessment, at any itacitinib dose level), the null hypothesis (CR rate of 5% or lower with the new combination) will be considered as supported, and the study will be terminated. If there are no CRs in the first three (3) patients (week 8 or 16), we will suspend the study enrollment and await final response assessment on all 9 patients (6 in Phase I and 3 in Phase II). The study will be considered successful if the total number of subjects with CR is ≥ 2 in Phase II (at the 8 week or 16 week response assessment).

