3.1.3 Study Intervention Phase II

Subjects with cHL will receive the recommended Phase II dose (RP2D) of itacitinib in combination with everolimus as determined in Phase 1. Phase II will enroll 8 to 17 subjects depending on Cohort expansion in the Phase I portion. Since 6 of the Phase I subjects will be recruited, treated and followed in the same way as the Phase II subjects, they will be considered as accrued to the Phase II study as well. At least 14 subjects will be treated at RP2D level and evaluable for CR rate. Using a Simon 2-stage optimal design, if there are no responders with CR by the 16 week response assessment from the first 9 evaluable subjects at the RP2D, the null hypothesis will be considered as supported, and the study will be terminated. If there are no CRs in the first several patients (week 8 or 16 assessment), we will suspend the study enrollment and await final response assessment on all 9 patients (until week 16). The study will be considered successful if the total number of subjects with CR is \geq 2 in Phase II.

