7 STATISTICAL PLAN

7.1 Sample size

Sample size determination: Utilizing 3 + 3 design, 6 to 15 subjects will be enrolled to Phase I portion of the trial (with at least 6 subjects treated at RP2D). Phase II will enroll 8 to 17 subjects depending on expansion needs in the Phase I portion. At least 14 subjects will be treated at RP2D level and evaluable for CR rate. The sample size for phase II was based on a decision between 2 pre-specified hypotheses about the probability of CR rate (p). The null hypothesis H₀: p = 5% reflects a response rate that would be of no clinical benefit compared to everolimus alone, and the alternative hypothesis H_a: p = 25% is a CR rate that might lead to larger, confirmatory studies. Using a Simon 2-stage optimal design, a total of 17 subjects at RP2D will be needed for 80% power at 1-sided alpha = 0.05 level. If by the 16 week visit there are no responders with CR from the first 9 evaluable subjects (at any itacitinib dose level), the null hypothesis will be considered as supported, and the study will be terminated.

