8.7 Stopping Rules (safety and efficacy)

The safety analysis is based on Bayesian probability calculations and will be performed after the first 6 subjects treated at the RP2D and then after enrollment of 9, 12, and 15 subjects at RP2D dose. The maximum rate of unacceptable toxicity (AEs that would fit the definition of DLT from phase 1 at any point or AEs that do not allow the subject to restart treatment within 28 days) is 30% and a beta prior of (1,5) is assumed (that is 1 unacceptable toxicity in 6 subjects). The study will be terminated if 4 unacceptable toxicities in 6 subjects, 5 in 9, 6 in 12, or 7 in 15 are observed. The posterior probability that the true rate of unacceptable toxicities is above 30% at each stopping would be around 77 to 79% (79%, 78%, 78%, and 77%, respectively).

The efficacy analysis is based on Simon 2 stage optimal design and will be performed after the enrollment of the first 9 evaluable subjects treated at the RP2D. If there are no responders with CR from the first 9 evaluable subjects (at the 8 week or 16 week response assessment, at any itacitinib dose level), the null hypothesis (CR rate of 5% or lower with the new combination) will be considered as supported, and the study will be terminated. The study will be considered successful if the total number of subjects with CR is ≥ 2 in Phase II (at the 8 week or 16 week response assessment).

If there are two (2) study related deaths during the phase I portion of the trial, the study will be terminated.

Any death in the Phase II portion will result in pausing enrollment of the study until investigation is completed. If there are two (2) study related deaths in the Phase II portion of the study will be terminated.

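### The stage 1 futility set (RP2D only or any itacitinib dose) and the CR window in the success rule (week 8/16 or best response) are each written in two incompatible ways

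*Combined protocol and SAP*

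**What the plan says.** **Futility set (no CR in the first 9 evaluable subjects stops the trial)**

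| Place | Who the nine are |
|---|---|
| 3.1.3 | RP2D only: "if there are no responders with CR by the 16 week response assessment from the first 9 evaluable subjects at the RP2D" |
| 7.1 | Any dose: "responders with CR from the first 9 evaluable subjects (at any itacitinib dose level") |
| 7.2.1 | Any dose: "first 9 evaluable subjects (at the 8 week or 16 week response assessment, at any itacitinib dose level") |
| 8.7, first efficacy sentence | RP2D only: "will be performed after the enrollment of the first 9 evaluable subjects treated at the RP2D" |
| 8.7, next sentence | Any dose, in the same words as 7.2.1 |
| Study Summary | No dose named |

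The design itself is stated for one dose: "a total of 17 subjects at RP2D will be needed for 80% power at 1-sided alpha = 0.05 level" (7.1). Section 7.2.1 describes the nine as "await final response assessment on all 9 patients (6 in Phase I and 3 in Phase II"), and 3.1.3 says of six Phase I subjects that "they will be considered as accrued to the Phase II study as well".

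**Success rule (at least 2 CRs)**

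Sections 7.2.1 and 8.7 count CRs "in Phase II (at the 8 week or 16 week response assessment"). Section 7.4 counts subjects whose best overall response is CR, with no time limit, and the primary endpoint in 3.3.2.1 is defined the same way. Section 3.1.3 and the Study Summary give no window. Under 6.7, imaging continues every 16 weeks after week 16.

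**Evaluability**

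The Study Summary asks for at least 21 days of therapy and one efficacy evaluation. Section 7.7 asks only for the 21 days.

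**The concern.** These are the stop/go and success rules of the primary Phase II test. A Simon design assumes that the stage 1 subjects are the first part of the final sample. If subjects at another dose fill stage 1, they can keep an inactive RP2D going or, if their dose is less active, help to stop an active one.

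The success rule has a similar gap. With one CR by week 16 and a second first seen later, the trial succeeds under 7.4 and fails under 7.2.1 and 8.7. The team would then have to choose a rule, possibly after seeing the data, in a single-arm trial whose credibility rests on a pre-specified rule.

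**Working it through.** **1. The plan's own design.** Inputs from 7.1: null CR rate 5%, alternative 25%, one-sided alpha 0.05, power 80%. An exhaustive search for the Simon optimal design returns 9 subjects in stage 1 (stop at 0 CRs) and 17 in total, with success at 3 or more CRs: alpha 0.047, power 0.812. The 9 and the 17 are reproduced. The written cut-off of 2 CRs gives alpha 0.172 and power 0.902. That is a separate problem, but the written cut-off is used below.

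**2. How many of the nine are at the RP2D.** Table 1 (3.1.2), all subjects evaluable, first nine in order of enrolment:

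| Path to Phase II | At RP2D | Dose of the others |
|---|---|---|
| Cohort 1: 1/3, then 0/3 DLTs | 9 | none |
| Cohort 1 (3 subjects), then Cohort 2 is the RP2D | 6 | lower |
| Cohort 1 stops at 3, then Cohort -1 | 6 | higher |
| Cohort 2 stops at 3, back to Cohort 1 | 6 | higher |
| Cohort 1 goes to 6, then Cohort -1 | 3 | higher |
| Cohort 2 goes to 6, back to Cohort 1 | 3 | higher |
| Cohorts 1, 2, 1, then -1 | 0 | higher |

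Everolimus is 5 mg throughout, so only the itacitinib dose differs.

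**3. Formula.** Let *k* of the nine be at the RP2D (CR rate *p*) and 9 − *k* at another dose (rate *q*, assumed).

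- Stop = (1 − p)^k × (1 − q)^(9 − k)
- Success = P(X₁₇ ≥ 2) − Stop × P(X₁₇₋ₖ ≥ 2), with X binomial at rate *p*

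Reference, *k* = 9:

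- *p* = 25%: stop = 0.75^9 = 0.075; success = 0.950 − 0.075 × 0.633 = 0.902.
- *p* = 5%: stop = 0.95^9 = 0.630; success = 0.172.

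**4. Active RP2D (*p* = 25%)**

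| k | q | False stop | Power |
|---|---|---|---|
| 6 | 25% | 0.075 | 0.890 |
| 3 | 25% | 0.075 | 0.882 |
| 6 (lower-dose path) | 15% | 0.75^6 × 0.85^3 = 0.109 | 0.862 |
| 6 (lower-dose path) | 5% | 0.75^6 × 0.95^3 = 0.153 | 0.827 |
| 6 (higher-dose path) | 30% | 0.061 | 0.901 |
| 3 (higher-dose path) | 30% | 0.050 | 0.905 |

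A false stop of 0.159-0.310 with *k* = 3 needs *q* = 15% down to 5% at the higher dose, that is, a higher dose that is less active. Nothing in the documents supports that.

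**5. Inactive RP2D (*p* = 5%), higher-dose paths**

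| k | Correct stop, q = 25% | False success, q = 25% | Correct stop, q = 15% |
|---|---|---|---|
| 9 | 0.630 | 0.172 | 0.630 |
| 6 | 0.95^6 × 0.75^3 = 0.310 | 0.208 − 0.310 × 0.102 = 0.176 | 0.451 |
| 3 | 0.95^3 × 0.75^6 = 0.153 | 0.184 | 0.323 |
| 0 | 0.75^9 = 0.075 | 0.192 | 0.232 |

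**6. How often each path occurs.** Among trials that reach Phase II, with an assumed DLT rate equal at every dose and 0-1 DLTs in 6 accepted as the RP2D:

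| DLT rate | All nine at RP2D | Lower-dose path | Higher-dose paths |
|---|---|---|---|
| 10% | 18% | 65% | 17% |
| 20% | 22% | 38% | 40% |
| 30% | 22% | 21% | 57% |

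**7. CR window.** Best-response CR rate 25%, all 17 at the RP2D, futility at week 16 under both rules, and an assumed share of CRs first seen after week 16. The week-16 rule is the two-stage calculation at 25% × (1 − late share). The best-response rule needs at least one week-16 CR in the first nine and at least two CRs at any time in 17. Success under the first implies success under the second, so the difference is the share of trials with opposite verdicts.

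| Late share | Best response | Week 8/16 | Opposite verdicts |
|---|---|---|---|
| 10% | 0.879 | 0.865 | 1% |
| 20% | 0.848 | 0.815 | 3% |
| 40% | 0.755 | 0.668 | 9% |

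**The case against.** - **A reconciling reading exists.** The any-dose phrase could mean subjects who started at the RP2D and were later dose-reduced. The count of 6 plus 3 in 7.2.1 and the 17 at the RP2D in 7.1 lean that way. But no section says so, and 7.1 and 7.2.1 place no RP2D limit on the nine. This supports the direction of the fix, not leaving the text alone.
- **Type I error barely moves.** A futility look can only lower false success. Under the reproduced boundary of 3 CRs, alpha is at most 0.0503 with no look at all. This stands: the loss is in early stopping and, to a lesser degree, in power.
- **The largest figures need a fivefold gap** between 5% at the RP2D and 25% at the next dose, which no section supports. With *q* = 10%, correct stopping is 54% (6 of 9) or 46% (3 of 9). This also stands, so the figures are illustrations.
- **Path counts are soft.** Subjects with a DLT may not reach 21 days. If two drop out when Cohort 1 stops at 3, then 8 of 9 are at the RP2D and correct stopping is 50%, not 31%. Table 1 gives no action for 0/3 followed by 1/3 in Cohort 2, so an assumption was needed there.
- **The window conflict is small.** Sections 3.3.2.1 and 7.4 agree on best response, and verdicts differ in 1-3% of trials unless late CRs are common.

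These points limit the size. They do not remove the two contradictions.

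**Conclusion.** The concern holds. The futility set has two incompatible definitions, side by side in 8.7, and so does the CR that counts towards success. The case for correction rests on that conflict, not on any one effect size.

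The dose issue has no effect when all nine are at the RP2D and little when both doses have the same CR rate (power 88-89% instead of 90%). On the lower-dose path, power stays above the planned 80% under the written cut-off. The more serious consequence is on higher-dose paths, where the look loses much of its ability to stop an inactive RP2D. False success there rises only from 17.2% to 17.6-19.2% with *q* = 25%, so the cost is mainly continued treatment at an inactive dose. All CR rates, DLT rates and late-CR shares are assumptions, because the documents give none for this combination.

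**What to change.** - **7.1, 7.2.1, 8.7:** replace the any-dose phrase with *at the RP2D, including Phase I subjects treated at the RP2D*. Add *at the RP2D* to the futility sentence in the Study Summary.
- **Futility look:** keep week 16.
- **Success rule:** use the stated primary endpoint, best overall response. Delete the week 8/16 restriction from the success sentences in 7.2.1 and 8.7, state a data cut-off in 7.4, and report CR by week 16 as a sensitivity analysis.
- **7.7:** align the evaluability definition with the Study Summary.

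**Cost.** These are text changes only. The futility look comes 3, 6 or 9 subjects later when 6, 3 or 0 of the nine would have been at the RP2D. It comes 12 later on the one Table 1 path that needs 3 + 6 + 3 + 6 = 18 Phase I subjects, above the stated 6 to 15. The final verdict waits for the data cut-off. Week-16 futility combined with best-response success also costs power if CRs come late: 75% at a 40% late share under the written cut-off, or 79.5%, 77% and 69% at 10%, 20% and 40% late if 3 CRs were required. The protocol should acknowledge this. None of these changes repairs the cut-off of 2 CRs (alpha 0.172), which needs its own correction.

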7.2.2 Interim Safety Analyses

The safety analysis is based on Bayesian probability calculations and will be performed after the first 6 subjects treated at the RP2D and then after enrollment of 9, 12, and 15 subjects at RP2D dose. The max tolerated DLT (see section 3.2) rate is 30% and a beta prior of (1,5) is assumed (that is 1 DLT in 6 subjects). The study will be terminated if 4 DLTs in 6 subjects, 5 in 9, 6 in 12, or 7 in 15 are observed. The posterior probability that the true DLT rate is above 30% at each stopping would be around 77 to 79% (79%, 78%, 78%, and 77% respectively).

If there are two (2) study related deaths in the phase I portion, the study will be terminated.

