A DLT will be defined as the occurrence of any toxicities in Table 2 occurring up to and during Day 28 of Cycle 1, except those with a clear alternative explanation (e.g., disease progression) or transient (≤ 72 hours) abnormal laboratory values without associated clinically significant signs or symptoms based on investigator and sponsor determination. All DLTs will be assessed by the investigator using CTCAE v5 criteria (NCI 2018). In order to be included in the tolerability review, subjects must have received the cohort-specific dose of itacitinib and everolimus for at least 75% of the days during the 28-day surveillance period of Cycle 1 or have experienced a

Itacitinib + everolimus in HL
Version 11.0
Page 16 of 72

	DLT. Additional subjects may be enrolled to achieve a minimum cohort size should withdrawal or dose interruptions/reductions result in subjects being non-evaluable. The maximum tolerated DLT rate is set to be 30%. During Phase II portion of the study, a Bayesian stopping rule will be employed to monitor excess DLT rate. Under the assumption of a beta prior of (1,5), that is 1 DLT in 6 patients, the study will be stopped if 4 in 6, 5 in 9, 6 in 12, or 7 in 15 DLT are observed during cycle 1 in phase II of the study. The posterior probability that the true DLT rate is above 30% at each stopping would be around 77 to 79%.
	Subjects who experience a DLT or an unacceptable toxicity (i.e. not able to resume therapy within 28 days due to unresolved toxicity) beyond the DLT window will be also considered in the determination of the RP2D dose.
	Any grade 5 hematologic and non-hematologic event related to the study treatments (at any time) will be considered a DLT.
Data and Safety Monitoring Plan	This study will be monitored according to the Sponsor Data and Safety Monitoring Plan.

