3.1.2 Study Intervention Phase I

Utilizing 3 + 3 design, 6 to 15 subjects will be enrolled to Phase I portion of the trial (with at least 6 subjects treated at RP2D). The starting dose of itacitinib will be 300 mg once daily (QD) in combination with everolimus 5 mg QD. Depending on tolerability, the dose of itacitinib in combination with everolimus could be increased to 400 mg QD (Cohort 2) or decreased to 200

Itacitinib + everolimus in HL
Version 11.0
Page 25 of 72

mg QD (Cohort -1). There will be no intra-patient dose escalations in phase I. The dose of everolimus will remain 5 mg QD for each cohort.

Additional subjects may be enrolled to achieve a minimum cohort size should withdrawal or dose interruptions/reductions result in a subject being non-evaluable. Dose cohorts are outlined in Table 1, and the design is depicted in Figure 1.

[figure not shown]
Subjects who experience a DLT or an unacceptable toxicity (i.e. not able to resume therapy within 28 days due to unresolved toxicity) beyond the DLT window will be also considered in the determination of the RP2D dose.

Table 1: Dose Cohort Design

Cohort	Subjects	Regimen	DLTs	Action
-1	0-6	Everolimus 5 mg QD	0/6	Begin Phase 2 at Cohort -1 dose
		itacitinib 200 mg QD	1/3	Enroll 3 additional subjects (6 total) at Cohort - 1 level; if no additional DLT, begin Phase 2 at Cohort -1 dose; if 1 or more additional DLTs, terminate study
			≥ 2	Terminate study
1	3-6	Everolimus 5 mg QD	0/3	Escalate to Cohort 2 dose
(starting dose)		itacitinib 300 mg QD	1/3	Enroll 3 additional subjects (6 total) at Cohort 1; if no additional DLT, begin Phase 2 at Cohort 1 dose; if 1 or more additional DLTs, de-escalate to Cohort -1
			≥ 2	De-escalate to Cohort -1
2	0-6	Everolimus 5 mg QD	0/6	Begin Phase 2 at Cohort 2 dose
		itacitinib 400 mg QD		Enroll 3 additional subjects at Cohort 2 (6 total);
			1/3	if no additional DLT, begin Phase 2 study at Cohort 2 dose; if 1 or more additional DLTs, treat 3 more patients on Cohort 1 dose, if 0-1 DLTs on Cohort 1, then RP2D is Cohort 1, if ≥ 2 DLTs on Cohort 1, then de-escalate and treat 6 patients at Cohort -1; if 0-1/6 have DLTs – the RP2D is Cohort -1, if ≥ 2 DLTs, then study is terminated
			≥ 2	Treat 3 more patients on Cohort 1 dose (6 total), if 0-1 DLTs on Cohort 1, then RP2D is Cohort 1, if $\geq 2/3$ DLTs on Cohort 1, then reduce to Cohort -1 and treat 6 patients. If 0-1/6 of Cohort -1 have DLTs – then RP2D is Cohort -1, if ≥ 2 DLTs, then study is terminated

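### Under section 7.2.2 the 4/6 and 5/9 safety looks cannot fire on Cycle 1 DLTs, because Table 1 has already limited the first six RP2D subjects to one DLT

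*Combined protocol and SAP*

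**What the plan says.** Section 7.2.2 schedules the safety analyses "performed after the first 6 subjects treated at the RP2D and then after enrollment of 9, 12, and 15 subjects at RP2D dose". The boundary is: "The study will be terminated if 4 DLTs in 6 subjects, 5 in 9, 6 in 12, or 7 in 15 are observed". The event is the section 3.2 DLT, the maximum tolerated rate is 30%, and the prior is Beta(1,5). The posterior probabilities of exceeding 30% at the four boundaries are given as "around 77 to 79% (79%, 78%, 78%, and 77% respectively").

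Four other places determine who the first six subjects are and how many DLTs they can have had:

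- The synopsis, section 3.1.2 and section 7.1 require at least six subjects at the RP2D in Phase I.
- Section 3.1.3 says of six Phase I subjects that "they will be considered as accrued to the Phase II study as well".
- Section 7.2.1 describes the first nine in the same way: "await final response assessment on all 9 patients (6 in Phase I and 3 in Phase II").
- Table 1 governs selection. For Cohort 1 after one DLT in three the rule is "if no additional DLT, begin Phase 2 at Cohort 1 dose; if 1 or more additional DLTs, de-escalate to Cohort -1". The other routes also end at no more than one DLT in six. Section 3.2 bases these decisions on events through Day 28.

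The rule is stated twice more, with differences. Section 8.7 keeps the same looks and boundaries but counts unacceptable toxicity: DLT-type events at any time, or events that prevent a restart within 28 days. The synopsis (Safety Evaluations) ends its list with "7 in 15 DLT are observed during cycle 1 in phase II of the study".

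**The concern.** A toxicity rule for Phase II should catch a dose that got through a six-subject Phase I cohort by chance. Under 7.2.2 the rule begins by re-counting the six subjects whose low DLT count made the dose the RP2D. Its first look asks for at least four events in a group that can contain at most one. The later looks carry the same six favourable results in their denominators.

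The plan describes the rule only by its posterior probabilities at the boundary. Those are unaffected by Phase I selection, so a reader could take the rule to be considerably more sensitive than it is.

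**Working it through.** **Inputs.** Looks at n = 6, 9, 12 and 15 with boundaries 4, 5, 6 and 7; prior Beta(1,5); threshold 30% (all section 7.2.2). At most 1 DLT in the first 6 (Table 1). True DLT rate p is assumed over a range.

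**Step 1: the plan's own figures.** With x DLTs in n subjects the posterior is Beta(1+x, 5+n−x). P(rate > 0.30) is:

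- 4/6, Beta(5,7): 0.7897
- 5/9, Beta(6,9): 0.7805
- 6/12, Beta(7,11): 0.7752
- 7/15, Beta(8,13): 0.7723

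These match the stated 79%, 78%, 78% and 77%.

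**Step 2: what each look needs, starting from 1/6.**

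- n = 6: needs 4; the count is 1. Impossible.
- n = 9: needs 5; the largest possible count is 1 + 3 = 4. Impossible.
- n = 12: needs at least 5 DLTs in 6 new subjects.
- n = 15: needs at least 6 DLTs in 9 new subjects.

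From 0/6 the last two requirements become 6 of 6 and at least 7 of 9.

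**Step 3: chance of stopping by subject 15.** Worked example from 1/6 at p = 0.30:

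- Look at 12: P(Bin(6, 0.3) ≥ 5) = 6(0.3⁵)(0.7) + 0.3⁶ = 0.0109.
- Look at 15, first firing there: P(4 of 6) × P(≥ 2 of 3) + P(3 of 6) × P(3 of 3) = 0.0595 × 0.216 + 0.1852 × 0.027 = 0.0179.
- Total: 0.0288, or 2.9%.

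The same exact recursion gives the table. The last column applies only 4/6 and 5/9 to new Phase II subjects, so it also uses nine new subjects.

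| True DLT rate | Current rule, from 1/6 | Current rule, from 0/6 | 4/6 and 5/9 in new subjects |
|---|---|---|---|
| 20% | 0.4% | <0.1% | 1.7 + 1.05 = 2.8% |
| 30% | 2.9% | 0.5% | 7.05 + 4.88 = 11.9% |
| 40% | 10.7% | 2.6% | 17.9 + 11.7 = 29.6% |
| 50% | 26.6% | 9.2% | 34.4 + 18.6 = 52.9% |
| 60% | 49.5% | 23.5% | 54.4 + 20.9 = 75.3% |

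(Component sums may differ in the last digit through rounding.)

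**Step 4: how often such a dose gets through.** Treating selection as at most 1 DLT in 6, P = (1−p)⁶ + 6p(1−p)⁵. This is 42% at p = 30%, 23% at 40%, 11% at 50% and 4% at 60%. Given passage, the current rule stops 2.2%, 9.1%, 24.1% and 46.9% of the time. The chance of passing and then not being stopped by subject 15 is 0.2333 × (1 − 0.091) = 21% at 40%, 0.1094 × (1 − 0.2408) = 8% at 50% and 0.0410 × (1 − 0.4686) = 2% at 60%.

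**Step 5: the section 8.7 reading.** Late events in the same six subjects count here. The documents give no late-event rate, so let q be an assumed chance for each of the five subjects without a DLT. From 1/6, reaching 4/6 has probability P(Bin(5, q) ≥ 3): 0.9% at q = 10%, 5.8% at 20%, 16.3% at 30% and 31.7% at 40%.

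**The case against.** The strongest reply is that the plan does not consist of 7.2.2 alone. A reader might infer that the early looks are dead under every statement of the rule, and the documents do not support that. Section 8.7 counts toxicity at any time, so late events in the same six subjects can reach 4/6 or 5/9. The synopsis wording can be read as newly enrolled subjects only, in which case 4/6 can fire. Section 3.2 makes a related grade 5 event a DLT whenever it occurs. Three late deaths, enough to move 1/6 to 4/6, would already have met a two-death rule, but one late death plus three DLTs in three new subjects would reach 5/9. Section 3.2 also allows a lower RP2D to be set later, and the first six at that dose might not have passed Table 1. Section 4.5 speaks of 3 to 6 Phase I subjects at the RP2D, against at least six elsewhere. All of this stands, and it confines the finding to Cycle 1 DLTs under 7.2.2 with six Phase I subjects counted.

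Three further inferences also go too far:

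- **That subjects have no protection until twelve are treated.** Section 8.7 pauses enrolment after any Phase II death and terminates after two study-related deaths, and section 8.8 refers to a monitoring plan.
- **That the loss is the gap to the same boundary without Phase I selection** (19%, 47%, 75% and 92% at 30% to 60%). That comparison ignores the toxic doses Table 1 itself rejects, as step 4 shows.
- **That the Phase I data are used twice because the prior equals one DLT in six.** The plan calls this prior assumed and never says it represents the Phase I result.

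**Conclusion.** The concern holds for section 7.2.2. With section 3.2 DLTs judged in Cycle 1 and the six Phase I RP2D subjects counted first, the 4/6 and 5/9 looks have probability zero for any dose that passed Table 1. The two later looks stop a dose with a true rate of 30% to 40% no more than about 11% of the time. At 50% and 60% they are less feeble (26.6% and 49.5% from 1/6), but doses that toxic seldom pass Table 1. The case that matters most is a true rate near 40%: about 23% of such doses pass, and about 9% of those are then stopped.

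The posterior figures are right; what is missing is the rule's behaviour given Phase I selection. The synopsis, 7.2.2 and 8.7 also disagree on which events and which subjects count, and that must be settled whichever text is meant to govern. The stopping probabilities assume independent subjects with a common DLT rate.

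**What to change.** 1. Reconcile the synopsis, 7.2.2 and 8.7 on one event window and one denominator. The choice of event window is for the sponsor.
2. Apply the existing boundaries to subjects newly enrolled in Phase II, as the synopsis wording indicates: 4/6 and 5/9, with 6/12 and 7/15 only if Phase II enrols that many new subjects. Sections 3.1.3 and 7.1 give 8 to 17, section 4.5 gives 11 to 17, and 17 at the RP2D less 6 from Phase I leaves 11. With 11 new subjects the looks at 12 and 15 are not reached; with only 8, neither is the look at 9. State the intended number.
3. Report the chance of stopping over a range of true rates, conditional on the dose having passed Table 1, beside the posterior probabilities.

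A further look at three new subjects is not needed. Stopping at 3/3 would raise the total at a true rate of 50% only from 52.9% to 53.7%.

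The change is to wording plus a short table, with no extra subjects or assessments. The real cost is more stopping of doses at or below the tolerated maximum: compared with the current rule from 1/6, from 0.4% to about 3% at a true rate of 20%, and from 2.9% to about 12% at 30%. The sponsor should accept that trade explicitly.

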3.2 DLT Definition

A DLT will be defined as the occurrence of any toxicities in Table 2 occurring up to and including Day 28 of Cycle 1, except those with a clear alternative explanation (e.g., disease progression) or transient (≤ 72 hours) abnormal laboratory values without associated clinically significant signs or symptoms based on investigator and sponsor determination. All DLTs will be assessed by the investigator using CTCAE v5 criteria (NCI 2018). In order to be included in the tolerability review, subjects must have received the cohort-specific dose of itacitinib and everolimus for at least 75% of the days during the 28-day surveillance period of Cycle 1 or have experienced a DLT.

Individual subject dose reductions may be made based on events observed at any time during treatment with study drug (see Section 5.6); however, for the purposes of dose cohort escalation/de-escalation, expanding a dose cohort, and determining the RP2D, decisions will be made based on events that are observed from the first day of study drug administration through and including Day 28. A lower RP2D may subsequently be determined based on relevant toxicities that become evident after Day 28.

Subjects who experience a DLT or an unacceptable toxicity (i.e. not able to resume therapy within 28 days due to unresolved toxicity) beyond the DLT window will be also considered in the determination of the RP2D dose.

Any grade 5 hematologic and non-hematologic event related to the study treatments (at any time) will be considered a DLT.

Table 2: DLT defining toxicities

TOXICITY

Non-hematologic

- Any \geq Grade 3 non-hematologic toxicity, EXCEPT the following:
 - Transient (≤ 72 hours) abnormal laboratory values without associated clinically significant signs or symptoms.
 - Nausea, vomiting, and diarrhea adequately controlled with medical therapy within 48 hours.

Itacitinib + everolimus in HL
Version 11.0
Page 28 of 72

 Singular or non-fasting elevations in blood glucose (i.e., blood glucose excursions will be considered toxicities if fasting blood glucose is elevated on 2 separate sequential occasions).

Hematologic

- Grade 3 thrombocytopenia with bleeding.
- Grade 4 thrombocytopenia.
- Febrile neutropenia (ANC $< 1.0 \times 10^9$ /L and fever $> 101^\circ F/38.5^\circ C$).
- Grade 4 neutropenia that does not recover to \leq Grade 2 in \leq 3 days after interrupting study drug.
- Grade 4 anemia unresponsive to treatment for 3 days

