7.7 Subject Population for Analysis – Phase II

In order to be included in the tolerability review, a subject must have received the cohort-specific dose of itacitinib and everolimus for at least 75% of the days during the 28-day DLT surveillance period or have experienced a DLT. Additional subjects may be enrolled to achieve a minimum cohort size of 3, should withdrawal or dose interruptions/reductions result in a subject being non-evaluable. In order to be included in the efficacy evaluation, a subject must have received at least 21 days of study-specified therapy. Subjects who receive at least one dose of the combined treatment (itacitinib and everolimus) will be assessed for adverse events, survival and exploratory analyses (FACT-lym, resolution of B symptoms or pruritus).

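### The safety looks at 9, 12 and 15 RP2D subjects are triggered by enrollment, with no written requirement that the newest subjects have completed the 28-day DLT window that the boundaries assume

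*Combined protocol and SAP*

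**What the plan says.** Section 7.2.2 sets four safety looks. The first "will be performed after the first 6 subjects treated at the RP2D"; the others come "then after enrollment of 9, 12, and 15 subjects at RP2D dose". Section 8.7 repeats this timing. On the prior, Section 7.2.2 says that "a beta prior of (1,5) is assumed", with a maximum tolerated rate of 30%. The rule is: "The study will be terminated if 4 DLTs in 6 subjects, 5 in 9, 6 in 12, or 7 in 15 are observed". The stated posterior probabilities that the true rate exceeds 30% at these boundaries are 79%, 78%, 78% and 77%.

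Three other places bear on when a count is complete:

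- Section 3.2 defines a DLT as "any toxicities in Table 2 occurring up to and including Day 28 of Cycle 1".
- Section 7.7 admits a Phase II subject to the tolerability review only if dosed "for at least 75% of the days during the 28-day DLT surveillance period or have experienced a DLT".
- Section 7.2.1 suspends enrollment and waits for final response assessments before the efficacy decision. No equivalent wait is written for the safety looks.

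The event being counted also differs. The synopsis counts DLTs seen during cycle 1. Section 8.7 counts DLT-type toxicities at any time, and adverse events that prevent a restart within 28 days.

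**The concern.** The rule can terminate the trial, so the count fed into it should be defined. Within one sentence the trigger changes from subjects treated to subjects enrolled. A subject enrolled on the day of a look has had no exposure, and one enrolled in the previous 28 days has had only part of the window. Neither is yet evaluable under Section 7.7 unless a DLT has occurred. If such subjects still count towards 9, 12 or 15, they are treated as free of toxicity and a fixed boundary is harder to reach. At the 9 and 12 looks, a toxicity in the newest subjects would be acted on only after three more had been enrolled. After the 15 look no further look is planned, although Section 7.1 calls for 17 subjects at the RP2D.

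**Working it through.** **Inputs from the documents.** Prior Beta(1,5); threshold 30%; boundaries 4/6, 5/9, 6/12 and 7/15 (7.2.2, 8.7); DLT window of 28 days (3.2); enrollment of up to 28 subjects for 23 evaluable, over 3 years (synopsis).

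**Step 1: reproduce the stated posteriors.** With r events in n subjects, the posterior is Beta(1 + r, 5 + n − r), and P(rate > 0.30) is its upper tail.

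- 4 in 6: Beta(5,7), 0.790
- 5 in 9: Beta(6,9), 0.781
- 6 in 12: Beta(7,11), 0.775
- 7 in 15: Beta(8,13), 0.772

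These match 79%, 78%, 78% and 77%. The plan's figures are right, and they assume that all n outcomes are known.

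**Step 2: the posterior when the count is reached with one outcome pending.** Replace n by n − 1.

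- 5 in 8: Beta(6,8), 0.835
- 6 in 11: Beta(7,10), 0.825
- 7 in 14: Beta(8,12), 0.818

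The boundary then demands stronger evidence than the stated 77% to 78%.

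**Step 3: how many outcomes might be pending.** The documents do not say, so this is an assumption. Three years is about 1,096 days. With even accrual, 1,096/28 = 39 days between subjects and 1,096/23 = 48 days. The average number inside a 28-day window is 28/39 = 0.7 or 28/48 = 0.6. If a look is made on the day of enrollment, one pending (the newest subject) is the minimum and the likely case. Two pending is shown as a sensitivity case.

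**Step 4: probability of stopping.** Let k outcomes be pending at the 9, 12 and 15 looks, with the six-subject look complete. The assessed numbers are 6, 9 − k, 12 − k and 15 − k, with boundaries 4, 5, 6 and 7. The chance of first crossing at each look comes from an exact binomial recursion over trials not yet stopped, and the four chances are added.

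| True rate | k = 0 | k = 1 | k = 2 |
|---|---|---|---|
| 30% | 0.19 | 0.15 | 0.11 |
| 40% | 0.47 | 0.38 | 0.30 |
| 50% | 0.75 | 0.66 | 0.57 |
| 60% | 0.92 | 0.88 | 0.81 |

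At 50%, the contributions by look are 0.344 + 0.186 + 0.129 + 0.090 = 0.749 for k = 0, and 0.344 + 0.078 + 0.135 + 0.107 = 0.664 for k = 1.

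**Step 5: condition on Phase I.** Section 3.1.3 counts six Phase I subjects towards Phase II, and Table 1 generally requires 0 or 1 DLT in six at the RP2D. On cycle 1 DLTs, 4/6 is then excluded. The 9 look cannot stop either, since 1 + 3 = 4 is below 5. At a 50% rate the chance of stopping is 0.096 + 0.145 = 0.241 with complete counts and 0.027 + 0.106, about 0.13, with one pending.

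**Step 6: re-apply the last boundary.** If 7/15 is checked again once those 15 subjects have matured, the one-pending figure at 50% rises from 0.66 to 0.73 (complete counts: 0.75). At 40% it rises from 0.38 to 0.44 (complete counts: 0.47).

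**The case against.** The strongest reply is that the plan can be read as using complete counts. The looks come after enrollment, which is not the same as on the day of enrollment. Section 7.2.1 uses similar wording for an efficacy look whose result is read at week 8 or 16, so the phrase may identify which subjects count rather than a calendar date. The boundaries are expressed as DLTs in 9, 12 or 15 subjects, the synopsis counts cycle 1 events, and Section 7.7 excludes immature subjects from the tolerability review. All of this stands. It shows what was probably intended, but no sentence makes a safety look wait.

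A reader might infer that the rule stops less often than the plan claims. The documents do not support that: they state no stopping probability, and the posteriors they do state reproduce. A reader might also infer that the boundaries will certainly be applied to incomplete counts. The text leaves this open.

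Counts are also cumulative. An event missed at 9 or 12 enters the next look, so the loss there is mainly delay. It becomes permanent only if 7/15 is never revisited. Other protections exist: SAE reports within 24 hours (8.4), and a pause after any Phase II death with termination at two study-related deaths (8.7). The death rules do not cover non-fatal DLTs.

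**Conclusion.** The point holds as a missing data-maturity condition: the written trigger does not secure the complete counts on which the boundaries and posteriors rest. With one outcome pending at each later look, the chance of stopping falls by about 0.08 to 0.09 at true rates of 40% to 50% before any conditioning (0.47 to 0.38, and 0.75 to 0.66). Given at most 1 DLT in the six Phase I RP2D subjects, it falls from 0.24 to 0.13 at 50%. The conditional figures describe this trial better if only cycle 1 DLTs count. If the last boundary is re-applied to the matured 15, most of the loss is delay.

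These sizes rest on an assumed number pending, independent outcomes with a common rate, and a complete six-subject look. The issue merits correction because the rule protects patients and the remedy is cheap. It is not evidence that the boundaries or posteriors are miscalculated.

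**What to change.** In Sections 7.2.2 and 8.7, state that each look is made when the first 6, 9, 12 or 15 RP2D subjects evaluable under Section 7.7 have all completed Day 28 of Cycle 1 or had a counted event. If a look is taken earlier, compute the posterior with the number actually assessed as the denominator. Say whether enrollment pauses while a look is awaited, and report the rule's stopping probabilities.

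Reconcile the counted event between the synopsis (cycle 1 DLTs) and Section 8.7 (toxicity at any time, or no restart within 28 days). A Day 28 wait completes only the cycle 1 count. If the wider definition is kept, the plan must say at what follow-up that count is taken.

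The cost is a few sentences in two sections, plus the reconciled definition. Each look moves by at most about 28 days, which is less than the 39 to 48 days between subjects at the planned accrual.
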